18.03.2021

**EVALUATION OF PRESSURE INJURY PREVENTION
CARE BUNDLE APPLICATION IN INTENSIVE CARE
UNIT PATIENTS DIAGNOSED WITH INTERNAL
DISEASES**

**STUDY PROTOCOL AND STATISTICAL
ANALYSIS PLAN**

NCT ID: Not yet assigned

STUDY PROTOCOL AND STATISTICAL ANALYSIS PLAN

Objective and Setting

The present study is a quasi-experimental study with a control group conducted in order to evaluate the application of pressure injury prevention care bundle in intensive care unit patients diagnosed with internal diseases.

Hypothesis

H0: The application of the pressure injury prevention care bundle is not effective in preventing pressure injury development.

H1: The application of the pressure injury prevention care bundle is active in preventing pressure injury development

Study Universe and Sample

The universe of the study consisted of patients hospitalized in the intensive care unit patients diagnosed with internal diseases in training and research hospital. The study sample was made up of diagnosed with internal diseases patients who were hospitalized in the intensive care unit between July-December 2021, who met the inclusion criteria, and who agreed to participate in the study. Power analysis was performed in order to determine the number of patients to be included in the study. The power of the test was calculated through G*Power 3.1 software. In order to determine the development status of pressure injuries in the intervention and control groups, 98 patients were included in the study with a minimum number of 49 patients in each group.

Inclusion and Exclusion Criteria

Patients who were 18 years old and above, who did not have any pressure injuries on any part of their body, who were expected to stay in the clinic for at least 24 hours, and who were diagnosed with an internal disease were included in the study. The patients who were younger than 18 years, who had a pressure injury on any part of their body, who were expected to stay in the clinic for less than 24 hours, and who had intensive care indications other than an internal disease were excluded from the study.

The end criteria for the study was determined as follows;

- Death of the patient, reaching the desired number of patients, discharging the patient from the clinic, the development of pressure injury in the patient.

Data Collection Instruments

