A. Patient Information Form: The form prepared by the researcher includes questions inquiring about the sociodemographic and background information of the patients (age, gender, body weight, height, smoking and alcohol use), clinical characteristics (date of hospitalization, hospitalization diagnosis, duration of stay in intensive care unit, Braden risk assessment tool score, being provided with mechanical ventilation or not, medicines used, development and staging of pressure injury), and laboratory results (hemoglobin, hematocrit, blood glucose level, saturation, prealbumin value).

B. Pressure Injury Prevention Care Bundle Form: The form was developed by the researcher by benefiting from the Prevention and Treatment of Pressure Injury – 2019 Quick Reference Guide, European Pressure Injury Advisory Panel (EPIAP), and National Pressure Injury Advisory Panel (NPIAP) (2016) guidelines (**Figure 2**). The pressure injury prevention care bundle includes risk assessment (risk is assessed using braden risk scale, the assessment is carried out within the first 8 hours, then it's done every day, if there is a change in the status of the individual, it will be re-evaluated), skin assessment (the skin is evaluated for non-fading redness by printing, localized temperature, edema and humidity, it is evaluated in each shift or change of state, pressure zones in contact with the medical device are evaluated every 12 hours), skin care (the skin is clean and kept in normal humidity, the areas of the fritz are not rubbed vigorously, they are not massaged, every 8 hours the barrier feature protects the product and skin, the skin is protected from urine and fecal incontinence, sheets are kept clean, tense and dry), positioning (every two hours, the right-hand side-back-left-side position is given 30°, respectively, the pressure on the bone protrusions is reduced, the heels are prevented from touching the bed and are maintained), regulation of nutrition and liquid management (individual enteral or parenteral nutrition is provided, the patient's fluid intake is evaluated, dehydration is evaluated, weekly albumin/crp values are monitored) ^{1,6,9,10}

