Stage 2: After the training, the pressure injury prevention care bundle was applied to the patients in the intervention group who met the inclusion criteria until the determined number of patients was reached.

Stage 3: At this stage, it was examined whether any pressure injuries developed in the patients in the group who were applied the pressure injury care bundle, and the effectiveness of the pressure injury care bundle was evaluated.

Data Evaluation and Statistical Methods

The study data were analyzed through IBM SPSS V23 software. In the categorical comparison of the groups, Yates Correction, Fisher's Exact test, and Pearson χ^2 test were employed. In the two-group comparison of the normally distributed data, Independent Two Samples t test was used, while in the comparison of the data without normal distribution, Mann-Whitney U test was used.

The risk factors affecting the process of disease development were analyzed with Cox regression analysis. In the comparison of survival duration according to VOD status, Log Rank test was employed. The analysis results were presented as mean \pm standard deviation for the quantitative data and as frequency (percentage) for the categorical variables. Significance level was taken as $p<.05$.

Ethics

In conducting study, universal ethical rules as well as scientific principles were observed. As the use of human beings in the study required the protection of individual rights, the principles of Helsinki Declaration of Human Rights were also observed. Ethics board approval was obtained from the Health Sciences University Hamidiye Interventional Research Ethics Committee (**Decision No: 2021.03.18-33**) and institutional permission was taken from the hospital where the study would be conducted and Medical Specialty Education Authority. Moreover, before collecting the study data, each patient participating in the study or their legal custodian was informed about the content of the study and nurses, voluntary participation, and their verbal and written consents were taken.

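### The log-rank test is grouped by an undefined VOD status and cannot be run as written, and no stated comparison of bundle with control accounts for time at risk

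*Combined protocol and SAP*

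**What the plan says.** Data Evaluation and Statistical Methods contains two time-to-event statements. The first is "The risk factors affecting the process of disease development were analyzed with Cox regression analysis". The second is "In the comparison of survival duration according to VOD status, Log Rank test was employed".

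Group comparisons are described separately. For categorical data the sentence begins "In the categorical comparison of the groups, Yates Correction" and goes on to name Fisher's exact and Pearson chi-square tests. For quantitative data the plan gives the t test or the Mann-Whitney test.

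The study question is whether injury develops. The hypotheses are worded that way. The sample-size sentence is framed "In order to determine the development status of pressure injuries in the intervention and control groups", and under Stage 3 "it was examined whether any pressure injuries developed in the patients in the group who were applied the pressure injury care bundle".

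The end criteria are "Death of the patient, reaching the desired number of patients, discharging the patient from the clinic, the development of pressure injury in the patient". The Patient Information Form records "date of hospitalization, hospitalization diagnosis, duration of stay in intensive care unit", then the Braden score, ventilation, medicines, and whether an injury developed and its stage, as well as demographics and laboratory values. It lists no VOD variable, no injury date and no reason for exit.

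**The concern.** A log-rank test needs a grouping variable, a time origin, an event and a censoring rule. The plan gives a grouping variable that cannot be identified and none of the other three. A reader cannot tell what the resulting p-value would compare, and the choice is left open until after the data are in.

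The gap matters because of the design. Time at risk differs between patients under the end criteria. It may also differ between groups, because control recruitment was completed and the nurses trained before the bundle began: "After the training, the pressure injury prevention care bundle was applied to the patients in the intervention group". If stays in the two periods differ, the group observed for longer has more opportunity to develop an injury, whatever the bundle does. Length of ICU stay is collected, so a difference could be seen, but no stated group comparison takes it into account.

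**Working it through.** **Textual check.** The plan has no figure of its own on this point to reproduce. The check is whether each element of a survival comparison can be found.

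| Element | Log-rank sentence | Cox sentence |
|---|---|---|
| Grouping or covariate | VOD status: used once, undefined, no listed variable of that name | Risk factors; study group not named |
| Event | Not stated | Disease development; most naturally pressure injury, but not named |
| Time origin | Not stated | Not stated |
| Censoring | Not stated | Not stated |

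The bundle form records care items as yes or no, and the Braden tool is a risk score. Neither contains VOD. The two figures are cited for the study stages and the bundle form, so their absence from the text does not explain the term. The remaining group tests (chi-square family, t, Mann-Whitney) do not handle censored time.

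**Does the reading matter?** If VOD status means study group, the test compares bundle with control. If it means pressure injury status, the outcome becomes the grouping factor and survival must refer to some other event. These are different analyses, and nothing in the text decides between them.

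**Illustration of time at risk.** This does not measure the labelling defect. It shows what a yes/no comparison alone can cost if stays differ. From the plan: 49 per group and a 5% significance level (taken as two-sided, which the plan does not state). Assumed, because the documents give none: exponential injury and exit times, no bundle effect, exit independent of injury risk, and a control mean stay of 10 days.

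With injury hazard h per day and mean stay m days, the probability of an observed injury is h / (h + 1/m). At h = 0.03:

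- m = 10: 0.03 / 0.130 = 0.231, or 49 × 0.231 = 11.3 expected injuries
- m = 8: 0.03 / 0.155 = 0.194, or 9.5
- m = 6: 0.03 / 0.197 = 0.153, or 7.5

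The groups differ in injury proportion with no bundle effect at all. False rejection rates from 20,000 simulated trials per cell (Monte Carlo standard error √(0.05 × 0.95 / 20,000) = 0.15 points at 5%, and 0.28 at 20%):

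| Hazard per day | Bundle mean stay (days) | Pearson | Yates | Log-rank by group |
|---|---|---|---|---|
| 1% | 10 / 8 / 6 | 6.0 / 6.9 / 11.7% | 1.7 / 1.9 / 3.6% | 4.8 / 4.9 / 5.0% |
| 3% | 10 / 8 / 6 | 5.0 / 7.6 / 17.0% | 2.8 / 4.4 / 11.1% | 5.0 / 5.0 / 5.1% |
| 5% | 10 / 8 / 6 | 4.9 / 8.1 / 20.3% | 3.0 / 5.4 / 14.7% | 5.3 / 5.1 / 5.1% |

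Inflation is small unless stays differ a good deal. The 1% Pearson row also overstates it. Expected injuries per group, averaged over the two groups, are only 4.5 / 4.0 / 3.6. If Fisher's test replaced Pearson whenever an expected count fell below 5 (an assumed rule; the plan states none), the rates would be 3.4 / 3.5 / 5.1%.

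**The log-rank test is not always safer.** Take an average hazard of 3% per day and no bundle effect, with half the patients at 0.3 times and half at 1.7 times that hazard. If only the low-risk bundle patients leave early (mean 3 days instead of 10), log-rank rejects in 11.8%, Pearson in 6.7% and Yates in 3.7%. At 6 days the figures are 6.3%, 5.5% and 3.0%.

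**Power with equal stays.** With a true hazard ratio of 0.5, 3% per day in control and 10-day stays, Pearson has 26.3%, Yates 17.9% and log-rank 28.8%. The gain from using time is small when stays are equal.

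**The case against.** The strongest reply is that the question is whether injury develops, that the stated categorical tests answer it, and that nothing in the plan promises a time-to-event comparison of the groups. That stands. A reader might infer that the hypothesis has no test or that the main analysis is invalid; the hypotheses, the sample-size sentence and the categorical comparison do not support that.

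A reader might also infer that the Cox model leaves the bundle out or models the wrong event. The sentence is silent on covariates and loose on the event. It excludes neither study group nor pressure injury, so it is imprecise rather than wrong.

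It may be said that VOD status is plainly a slip for study group. It may be, but the documents do not say so, and the definition should be asked for before a replacement is assumed. Conversely, it would go too far to say that no such status could be built from the collected data: diagnosis and medicines are recorded. What holds is that no variable of that name is listed. Nor is there any sign that the grouping was chosen after the data were seen; the plan only fails to rule it out.

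Three practical objections also stand. A log-rank test needs an injury date, which the form does not list. Discharge and death may be related to injury risk, in which case censoring at them can mislead, as the 11.8% figure shows. Finally, skin checks each shift are a bundle item and do not appear in the listed control routine, so injuries may be detected at different times in the two groups. These objections shape the fix but do not remove the defect.

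**Conclusion.** The concern holds in this form. A stated inferential test cannot be run as written, because its grouping variable is undefined and its time scale and event are not given. As a separate consequence of how the Cox sentence is worded, no stated comparison of bundle with control accounts for time at risk. This should be fixed but is not fatal, since the yes/no comparison still tests the hypothesis.

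The textual finding rests on no assumption. The simulated rates rest entirely on assumed hazards, stays and exit patterns. A reader might take the 17.0% or 20.3% as the expected error rate of this trial. The documents do not support that, because they give no injury rate or stay and nothing to suggest that bundle stays are 40% shorter.

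**What to change.** 1. Define or correct VOD status. If study group was meant, state: *Time from enrolment to first pressure injury is compared between bundle and control by log-rank test, censoring at discharge, death or end of study; the Cox model for pressure injury development includes study group.* If another variable was meant, define it and add this group comparison as well.
2. Confirm that the date of first pressure injury and the exit date and reason (injury, discharge, death, end of study) are recorded, and add them to the Patient Information Form if not. Length of stay cannot stand in for time to injury in a patient whose observation ends at the injury. Without injury dates the log-rank test cannot be run, and the categorical comparison remains the only group test; the plan should then say so.
3. Because discharge and death may be related to injury risk, report cumulative incidence of pressure injury by group alongside the log-rank test, with discharge and death as competing events.

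The cost is two sentences of analysis text and one additional display if the dates are already captured. If they are not, it also requires a small addition to the form, or retrieval from the clinical record where that is possible. The sample size and the main yes/no comparison are unchanged.
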